## 6.3 Definitions related to study Endpoints

### Resolution of Persistent Lymphopenia

Subjects who complete or drop out of a cladribine clinical trial with a Grade 3 or Grade 4 lymphopenia as defined by the Common Terminology Criteria for Adverse Events (CTCAE) [8] will be defined as having ‘persistent lymphopenia’ and will be monitored until lymphopenia resolves. Resolution is the achievement of a CTCAE Grade 1 or Grade 0 lymphocyte count.

According to the CTCAE version 4.03 [8], lymphopenia grades are defined as follows:

- Grade 1: < lower limit of normal (LLN) to 800/mm^3 or < LLN to 0.8 × 10^9/L
- Grade 2: < 800–500/mm^3 or < 0.8–0.5 × 10^9/L
- Grade 3: < 500–200/mm^3 or < 0.5–0.2 × 10^9/L
- Grade 4: < 200/mm^3 or < 0.2 × 10^9/L

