Data collected from last value from the end of clinical trial to the last ALC value in PREMIERE will be presented and summarized on a continuous manner (absolute value only) and by grade, over time.

ALC Registry Baseline is defined as the first ALC date with a value on or after the end of clinical trial +1 day [Registry Day 1].

Programming rule to cover possible unclean data:

If first ALC date in PREMIERE is before the end of clinical trial, ALC Registry Baseline is defined as the first ALC value in PREMIERE on or after the end of clinical trial + 1 day.

A new set of time window are presented below using visit window computed relative to ALC Registry Baseline.

If more than 1 value is available for a particular time window for the same subject, the first value in the time window will be considered.

Table 8 Time window for lymphocyte from the end of clinical trial

Evaluation	Interval for analysis (day)
Last value from last clinical trial	
ALC Registry Baseline	First ALC date with value in PREMIERE registry
Week 12	[2 - 98]
Week 24	[99 - 182]
Week 36	[183 - 266]
Week 48, 1y	[267 - 350]
Week 60	[351 - 434]
Week 72	[435 - 518]
Week 84	[519 - 602]
Week 96, y2	[603 - 700]
Week 144, y3	[701 - 1036]
Etc.	[1037 - weekN*7+4*7]

Lymphopenia grade and MS-DMD

Best and Worst ALC grades will be presented in relation to use of MS-DMD medication. For subjects with MS-DMD medications reported at least once after end of clinical trial, the best and worst ALC grade will be selected on or after (\geq) the first MS-DMD.

The Worst and the Best grade will be summarized overall and by treatment group. Subjects who are not taking MS-DMD from the end of clinical trial +1 day to the end of PREMIERE will be excluded from the analysis.

Resolution of lymphopenia computed with observed ALC value

Subjects who complete or drop out at the end of the clinical trial with an unresolved lymphopenia will be presented, together with their outcome in PREMIERE registry. The outcome can be resolved or unresolved.

An unresolved lymphopenia is defined for a subject who left the end of a clinical trial without returning to normal or grade 1 ALC value after an episode of grade 3 or 4 lymphopenia. A grade 3 or 4 lymphopenia episode is defined by a start/end date. Start= ALC \geq grade 3, post baseline, End = following normal (grade 0) or grade 1.

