The duration (in months) of the resolved episodes (out of the unresolved at end of clinical trial period) will be summarized. In addition, use of MS-DMDs prior to resolution will be presented.

Resolution of lymphopenia computed using CRF tick box

Reporting will be done for SAF. This is an exception, to include the largest possible information available.

The number of subjects with declared Grade 3 or 4 lymphopenia at end of clinical trial [CRF Tick box], will be summarized together with their outcome in PREMIERE. The outcome in PREMIERE will be computed from those with at least one grade 0/1 in PREMIERE or with a CRF "resolution date".

Presentation per treatment group and total will be done.

Resolution of lymphopenia based on observed ALC value versus CRF tick box

A 2-by-2 table of number of subjects with and without resolution of lymphopenia at the end of clinical trial based on ALC value versus CRF Tick box will be presented.

In addition, a listing will be generated for subjects with unresolved lymphopenia at the end of clinical trial according to ALC grade, but with the CRF Tick box = "Resolved". The following variables will be displayed: Subject ID, cumulative dose of cladribine, previous clinical trial, treatment group (see section 9.1), all ALC values in PREMIERE with grade and date and tick box for resolved with date of resolved if available.

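### The observed-ALC resolution table admits Grade 2 trial exits that the protocol does not, and closes an episode on one unconfirmed count at the same 0.8 line, with no relapse category

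*SAP*

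**What the plan says.** Protocol 6.3 defines persistent lymphopenia by the grade at trial exit: "Subjects who complete or drop out of a cladribine clinical trial with a Grade 3 or Grade 4 lymphopenia". Its resolution rule is a single attainment: "Resolution is the achievement of a CTCAE Grade 1 or Grade 0 lymphocyte count". Grade 1 runs down to 0.8 x 10^9/L, Grade 2 is 0.5 to below 0.8, and Grades 3 and 4 are below 0.5. SAP Table 6 uses the same cut-points.

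SAP 15.1.4 plans two resolution tables.

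- **Observed ALC.** A subject is unresolved on leaving the trial "without returning to normal or grade 1 ALC value after an episode of grade 3 or 4 lymphopenia". The episode closes at one value: "End = following normal (grade 0) or grade 1". The outcome is either resolved or unresolved, and the duration in months is summarised for resolved episodes only.
- **CRF tick box.** The denominator is "The number of subjects with declared Grade 3 or 4 lymphopenia at end of clinical trial [CRF Tick box". For the result, "The outcome in PREMIERE will be computed from those with at least one grade 0/1 in PREMIERE"; the sentence goes on to accept a CRF resolution date as well.

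SAP Table 1 declares that the life-table analysis is replaced by descriptive statistics and that the Kaplan-Meier analysis of episode duration, already in the integrated safety summary, will not be repeated. It does not mention a change in who counts as having persistent lymphopenia.

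**The concern.** Time to resolution of lymphopenia is one of the three primary endpoints. With the life table and Kaplan-Meier analyses dropped, this report is left with the resolved/unresolved split and the durations of resolved episodes. Both turn on the rule for a single count.

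In the observed-ALC table, once a Grade 3/4 episode has occurred, the 0.8 line decides both whether a subject is unresolved at exit and whether the subject later resolves. No minimum rise and no second value are required, and there is no category for a later fall. A subject who leaves at 0.78, reads 0.81 once and then reads 0.60 and 0.45 is reported as resolved. For a stable subject just below 0.8, measurement variation can only move the outcome towards resolved, and more counts make that more likely. The resolved proportion could then overstate recovery, and the summarised durations could be too short.

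The subjects most exposed to this are Grade 2 exits, whom protocol 6.3 leaves out of the endpoint population.

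**Working it through.** The plan states no resolution rate, variability or sample size for this endpoint, so there is no figure to reproduce. The check compares the definitions and then sizes the noise effect under stated assumptions.

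**1. Definitions side by side (ALC in 10^9/L)**

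| | Required at trial exit | Resolved when | Confirmation | Relapse category |
|---|---|---|---|---|
| Protocol 6.3 | below 0.5 | one value of 0.8 or more | none | none |
| SAP, observed ALC | earlier value below 0.5, no return to 0.8 | next value of 0.8 or more | none | none |
| SAP, tick box | declared Grade 3/4, i.e. below 0.5 | one value of 0.8 or more, or a CRF date | none | none |

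Only the observed-ALC row lets in exits from 0.5 to below 0.8. Only there do the entry and resolution lines coincide.

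**2. One subject, closed form**

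Assume a stable level m, independent lognormal variation around it and within-subject coefficient of variation CV.

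- s = sqrt(ln(1 + CV²))
- p = 1 − Φ(ln(0.8/m)/s)
- chance of at least one value of 0.8 or more in k counts = 1 − (1 − p)^k

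With CV 20%, s = sqrt(ln 1.04) = 0.198.

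- m = 0.70: ln(0.8/0.70) = 0.1335; 0.1335/0.198 = 0.674; p = 0.250; four counts give 1 − 0.750^4 = 68%.
- m = 0.45: ln(0.8/0.45) = 0.575; 0.575/0.198 = 2.91; p = 0.0018; four counts give 0.7%.

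**3. Averaged over subjects, by simulation**

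All of the following are assumptions: true ALC stable and lognormal (median 0.65, log-SD 0.35), restricted to below 0.8; lognormal error with mean 1; four later counts. The prior-episode rule is modelled as one to four earlier counts, at least one below 0.5 and none at 0.8 or above.

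| Exit group | CV 10% | CV 20% | CV 25% |
|---|---|---|---|
| Grade 2, conditioning on exit value only | 18% | 36% | 43% |
| Grade 2, with the prior-episode rule | about 0.2% | about 14% | about 23% |
| Grade 3/4 (protocol and tick-box population) | 0% | 6% | 14% |

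**4. Sensitivity**

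Centring the error on the median instead of the mean gives 18/38/46% for the first row, about 0.1–0.2/14–15/24–25% for the second and 0/7/15% for the third. A log-uniform true level from 0.2 to 0.8, without the prior-episode rule, gives 18/35/40% for Grade 2 exits and 0/2/4% for Grade 3/4 exits. With 14 counts, the number of follow-up contacts in protocol Appendix I, those become 31/58/65% and 0/4/9%.

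**5. Where later values appear**

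SAP 15.1.4 tabulates ALC by grade over time to the last registry value, in two sets of windows. It tabulates best and worst grade from the first MS-DMD, for MS-DMD users only. It lists all registry ALC values for subjects unresolved by ALC at trial end but ticked as resolved. None of these is linked to the resolution outcome, so a subject counted as resolved who later fell cannot be picked out as such.

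**The case against.** The strongest defence is that the single-value rule is the protocol's own definition. The SAP follows it, and the analysis is descriptive with no inference planned. This stands: asking for confirmation improves the display and does not correct a contradiction. It does not cover the admission of Grade 2 exits, which departs from protocol 6.3 and is undeclared.

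The documents do not support several stronger readings that a reader might infer.

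- *Entry and resolution share the 0.8 line in both tables.* They do not. Tick-box entry is below 0.5, so a subject must cross the whole Grade 2 band, and the 0.78 example never enters that table.
- *A single ALC is the only route to resolution.* In the tick-box table a CRF resolution date alone also counts.
- *Relapse is ignored.* That is true of the resolution outcome, but not of the whole SAP, as the ALC-by-grade tables show.
- *A third or more of Grade 2 resolutions are noise.* The higher percentages leave out the prior-episode rule, and they are shares of stable subjects, not of observed resolutions. Under a stable true ALC, applying the rule cuts them sharply, almost to nothing at CV 10%. If the true level rose after the nadir and then plateaued below 0.8, that conditioning would weaken, so the lower figures are not certain either.

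A last objection is that a rule requiring every later count to be Grade 0/1 has the opposite bias. With the same error model, a subject with a true ALC of 0.9 has about a 42–83% chance of at least one count below 0.8 among four. This stands, and it is why the added rows should be supplementary and should not redefine resolution.

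**Conclusion.** The concern holds for the observed-ALC table. That table widens the protocol's population to Grade 2 exits without declaring it, and for those subjects one count across a shared 0.8 line decides the outcome. Under the stated model with four later counts, noise alone would resolve about 0.2/14/23% of stable Grade 2 exits at CVs of 10/20/25% with the prior-episode rule, and about 18/36/43% without it.

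For the tick-box table the threshold argument largely falls away (about 0–14% in the same model). What remains there is that a later fall is not shown in the outcome and that date-only resolutions are not separated.

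These sizes rest on an assumed CV, an assumed spread of true levels, independent errors and no true recovery. The documents give neither the variability nor the number of Grade 2 exits, so the actual bias is unknown. The change is worth making because this is a primary endpoint and the remedy uses existing data.

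**What to change.** Keep protocol 6.3 resolution as the main row in both tables of SAP 15.1.4, and change the reporting around it.

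1. In the observed-ALC table, show Grade 3/4 exits (the protocol population) separately from Grade 2 exits. Add the widening to SAP Table 1 with a reason.
2. In both tables, add descriptive rows under resolved:
   - confirmed: the next count is also Grade 0/1;
   - later fall: any later count is Grade 2–4, stating whether an MS-DMD was started before it;
   - unconfirmed: no later count;
   - tick-box table only: resolution date without a Grade 0/1 count.

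   State that confirmed and later fall can overlap.
3. Summarise duration for all resolved episodes, as planned, and again for confirmed episodes.

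Use only counts already captured; no extra testing and no change to patient management is implied. The cost is SAP wording, a few lines of programming and some extra rows. Two limits need a footnote. Protocol 8.4 calls for counts only until resolution, so some subjects will be unconfirmed and the confirmed group is selected. The later-fall row itself grows with the number of counts.

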15.2 Secondary Endpoints: Pregnancy

Reporting will be done for SAF.

Data collection for pregnancy, pregnancy outcomes, including congenital malformations, spontaneous abortion, elective abortion, stillbirth, ectopic pregnancy, molar pregnancy, and other important health conditions in the offspring is a secondary endpoint of the PREMIERE registry with its dedicated questionnaire.

The number of subjects with pregnancy, treatment status at start of pregnancy, number of pregnancy and outcomes will be presented by treatment group together and split by female subjects and for male participant pregnancy of partner.

Treatment status at start of pregnancy will be summarized as follows:

- ≤ 6 months after end of treatment: defined as start of pregnancy \leq last dose + 183 days
- > 6 months after end of treatment: defined as start of pregnancy $>$ last dose + 183 days

For start of pregnancy, the first date of the last menstrual period will be used. If this date is missing or partial, the estimated delivery date will be considered (minus 280 days for duration of pregnancy). If that estimated delivery date is also missing, the date of baby birth and gestational age at birth will be considered.

Descriptive statistics will be presented for the time (in days) from last dose to start of pregnancy for subjects who started pregnancy \leq 6 months after end of treatment.

Mode of delivery, major delivery complication (y, n), infant child status (alive, deceased) and birth defects (y, n) will be presented.

A listing of AE related to pregnancy and a listing of pregnancy details will be presented.

All datasets with event collection of pregnancy, dedicated CRF pages or AE reporting or any other datasets will be considered as source of information. When information is taken from AE panels, all PTs from MedDRA SMQ (SMQ 20000185) labelled “SMQ 20000185 Pregnancy and neonatal topics” are identified (see Appendix 18.1). The obtained list is reviewed, and a decision is made for which events qualify as Pregnancies. These classifications are documented with reasons in Appendix 18.2 and read into the programs for calculations.

Note: the final list of AEs related to pregnancy may be revised after database lock. Any changes from the list above will be described in the CSR.

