*In the CLARITY trial, pregnant and breastfeeding women were specifically excluded and all female study participants were required to use adequate contraception throughout the duration of their participation in the trial. Male participants were also required to use contraception so that their partners did not become pregnant. Despite these protocol requirements, 24 pregnancies were reported in 23 of the 898 female subjects who participated in the CLARITY trial. Of these 24 pregnancies, 6 occurred among subjects who received treatment with placebo, 7 occurred among subjects randomized to the 3.5-mg/kg dose, and 11 occurred among subjects who randomized to the 5.25-mg/kg dose of cladribine. Information on the timing of pregnancies in relation to cladribine exposure in CLARITY indicated that of the 24 pregnancies, 6 pregnancies occurred while the subject was receiving treatment (i.e., within a 28-day treatment course), 17 pregnancies occurred while the subject was not receiving treatment, and 1 pregnancy occurred 6 months after the subject had completed the study.*

*Of the 24 pregnancies, 5 resulted in full-term normal live births (2 pregnancies in the 5.25 mg/kg cladribine dose group and 3 pregnancies in the placebo group). Both of the subjects in the cladribine 5.25 mg/kg group who delivered full-term normal babies had received 6 courses of cladribine tablets; conception had occurred approximately 2 weeks and 6 months, respectively, after the subjects had received their sixth course of therapy. Thirteen of the 24 pregnancies were terminated by elective abortions, 1 by therapeutic abortion due to choriocarcinoma, 4 pregnancies ended in miscarriage (3 in the cladribine treatment groups), and 1 pregnancy was ectopic. Although the Sponsor requested information on the terminations of these pregnancies, no postmortem examinations had been conducted.*

Limited information regarding the long-term safety of cladribine greater than 4 years is currently available. During clinical development, the cladribine Data Safety Monitoring Board (DSMB) recommended monitoring the long-term occurrence of malignancies and deaths, and pregnancy outcomes, in subjects exposed to cladribine.

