#### Maternal Information

- Contact information for the gynecologist-obstetrician or physician who follows the pregnancy
- Occupation, highest education level attained
- Maternal weight
- **Obstetrical history:** number of previous pregnancies and outcome (live birth, miscarriage, elective termination with specification of gestational length and context, late fetal death, ectopic pregnancy, molar pregnancy), previous maternal pregnancy complications, previous fetal/neonatal abnormalities and type, history of subfertility.
- **Maternal and medical history:** risk factors for adverse pregnancy outcomes including environmental or occupational exposures, e.g., hypertension, diabetes, seizure disorder, asthma, allergic disease, heart disease, depression or other psychiatric disorders, sexually transmitted diseases, hepatitis, AIDS (specify viral load, CD4 count), other.
- **Current pregnancy:** date of last menstrual period (LMP); pregnancy gestational age at the time of baseline interview (specify if based on ultrasound or LMP); estimated date of delivery; number of fetuses; treatment for infertility (specify); exposure to products subject to medical prescription, over-the-counter products, pregnancy supplements such as folic acid, multivitamins (name, dosage, and route; date of first use; date of end of treatment; duration) and indication; recreational drug use, e.g., tobacco, alcohol, illicit drugs (specify amount and if stopped during pregnancy); results of serology tests, e.g., rubella, toxoplasmosis; complications during pregnancy and date (including adverse drug reactions); disease course during pregnancy and any complications; antenatal checkups (specify dates and results), e.g., fetal ultrasound, serum markers (AFP, others), chorionic villi biopsy (CVS), amniocentesis.
- **Family history:** history of congenital abnormality, psychomotor retardation in the family (specify paternal/maternal and relationship), consanguinity between parents (specify degree).

**Pregnancy offspring:** For children born of female subject, a specific baseline interview will be conducted to capture information about congenital malformation and general health and development status. Contact data for the pediatrician or physician following the child will be obtained.

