### **Fetal Information**

To be collected in case of elective termination, spontaneous abortion, and late fetal death.

- Reason for termination
- Gestational age at termination
- Results of physical examination (gender, external anomalies) and pathology

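### The pregnancy-dating rule ends with a step that works only for births, so whether exposure timing is missing depends on how the pregnancy ended (minor)

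*SAP*

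**What the plan says.** SAP 15.2 sets a three-step rule.

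1. "For start of pregnancy, the first date of the last menstrual period will be used".
2. "If this date is missing or partial, the estimated delivery date will be considered (minus 280 days for duration of pregnancy").
3. "If that estimated delivery date is also missing, the date of baby birth and gestational age at birth will be considered".

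The date is used twice. It assigns each pregnancy to a treatment status, at most 183 days or more than 183 days after the last dose. It also feeds a descriptive summary of days from last dose to start of pregnancy, restricted to those within the 183 days.

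Pregnancies that do not end in a birth belong to the endpoint by name. SAP 15.2 lists "spontaneous abortion, elective abortion, stillbirth, ectopic pregnancy, molar pregnancy, and other important health conditions in the offspring is a secondary endpoint".

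SAP 9.12 allows no imputation of missing data. SAP 9.13 keeps missing observations in the denominator of a table and shows them as their own category.

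The protocol collects two dating items that the SAP rule does not use. Protocol 8.4, Fetal Information, lists "Gestational age at termination" for elective termination, spontaneous abortion and late fetal death. Protocol 8.3.1.4, Maternal Information, lists "pregnancy gestational age at the time of baseline interview (specify if based on ultrasound or LMP").

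**The concern.** The third step is a rescue for pregnancies that the first two steps fail to date, and it is open only to those that ended in a birth. Two pregnancies with identical gaps in LMP and estimated delivery date are therefore treated differently because of their outcome. One is assigned to a timing category and the other is not.

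The split at last dose + 183 days is the SAP's only classification of pregnancies by time since treatment. Protocol section 3 says that reproductive and developmental toxicity in humans cannot be excluded, so the timing of losses is part of what this endpoint is meant to show. If timing is missing more often for losses than for births, anyone who looks at dated pregnancies alone sees a selected set.

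A second weakness sits in the same rule. A partial LMP is set aside in favour of the estimated delivery date. If that is absent too, a month-only LMP is lost even when the month alone settles which side of the cut-off the pregnancy falls on.

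**Working it through.** The plan gives no figure to reproduce. The check is to trace the rule by outcome and then see what else is on file.

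**Trace.** Take a pregnancy with LMP missing or partial and estimated delivery date missing.

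| Outcome | Is step 3 usable? | Result |
|---|---|---|
| Live birth, birth date and gestational age recorded | Yes | Dated |
| Miscarriage or termination | No birth | Undated |
| Ectopic or molar pregnancy | No birth | Undated |
| Stillbirth | Unclear: the SAP does not say whether it counts as a birth, and the protocol puts late fetal death on the fetal form | Open |

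SAP 15.2 also lets all datasets serve as sources, but that sentence concerns finding pregnancies and adds no dating step. Step 3 starts only when the estimated delivery date is missing, so a partial delivery date has no rule.

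**Can both dates fail for a loss?** The documents leave room for it.
- The estimated delivery date is an item of the pregnancy questionnaires (Protocol 8.3.1.4 and 8.4). After year 2 contacts are yearly (Protocol 8.2), so a pregnancy can begin and end between contacts.
- For the lag interval, the records review lists LMP and outcome but no delivery date (Protocol 8.3.1.2). The questionnaire for subjects without accessible records lists no pregnancy item (Protocol 8.3.1.1).
- SAP 15.2 also takes pregnancies from adverse event data and from partners of male participants.

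**Could the losses be dated?** Often, from items already planned. Gestational age at termination is collected. An outcome date may come from the adverse event record: pregnancies are entered there (Protocol 8.5.3.1), and reports carry onset and resolution dates (Protocol 8.5.2). Outcome date minus gestational age is the same derivation as step 3 applies to births.

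**Partial LMP.** A month-only LMP leaves the category in doubt only if the calendar month contains last dose + 183 days. In every other month all possible dates lie on one side, and no day need be imputed.

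**Illustration only.** Let q be the share of pregnancies with neither date usable. The documents do not give q; assume 5% to 30%, equal across outcomes, with complete birth data. For a worked set, take the CLARITY pregnancies in Protocol section 3: "Thirteen of the 24 pregnancies were terminated by elective abortions", with 1 therapeutic abortion, 4 miscarriages, 1 ectopic pregnancy and 5 live births. The sum is 13 + 1 + 4 + 1 + 5 = 24, so 19 were not live births. Expected undated losses are 19q, and the chance of at least one is 1 − (1 − q)^19. All 5 births are dated.

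| q | Undated losses of 19 | Chance of at least one | Losses among dated pregnancies |
|---|---|---|---|
| 5% | 0.95 | 62.3% | 18.05/23.05 = 78.3% |
| 10% | 1.9 | 86.5% | 17.1/22.1 = 77.4% |
| 20% | 3.8 | 98.6% | 15.2/20.2 = 75.2% |
| 30% | 5.7 | 99.9% | 13.3/18.3 = 72.7% |

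With full dating the last column would be 19/24 = 79.2%. If a share g of the undated losses has both outcome date and gestational age, the extended step leaves q(1 − g) of losses undated. At q = 10% that is 5% for g = 0.5 and 2% for g = 0.8. At q = 30% it is 15% and 6%.

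**The case against.** The strongest reply is that little of what the SAP plans to report is harmed, and most of that reply stands.

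- A reader might infer that the outcome mix within each timing category will be biased in a planned table. The SAP does not support this. It presents treatment status and outcomes by treatment group, separately for female subjects and for partners of male participants, and specifies no cross-table of outcome by timing. An undated loss still counts among the outcomes.
- A reader might infer that the exposure classification itself is lost. It is not. The main classification is exposed or never exposed to cladribine (SAP 9.1), which needs no pregnancy date.
- A reader might infer that undated pregnancies disappear. Under SAP 9.13 they appear as missing, and a listing of pregnancy details is planned.
- A reader might infer that an early loss has no delivery date by nature. Step 2 uses the estimated date, which does not require a delivery. Two separate items must fail before the gap opens.
- A reader might take the 19 of 24 from CLARITY (79%) as the impact. Those pregnancies arose in a trial that required contraception, whereas the registry counts pregnancies from Registry Day 1. The figure also describes a step reached only after two others fail.

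The remedy has limits too. Protocol 6.3 measures gestational age from the LMP, so unless it came from ultrasound it may be missing with the LMP. The fetal form lists no outcome date and does not name ectopic pregnancy. An interview held after the loss gives no current gestational age. The case report form is not in the documents, so availability of the fields cannot be confirmed.

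None of this answers the narrower point. The rule dates a birth and leaves a loss undated on the same gaps, although the protocol plans to collect data that could date some of those losses.

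**Conclusion.** The point holds as a minor specification gap. For pregnancies with no complete LMP and no estimated delivery date, SAP 15.2 makes missing exposure timing depend on outcome. This affects the split at last dose + 183 days and the days-from-last-dose summary, from which undated pregnancies that began within the period drop out. It does not affect outcome counts, the comparison by treatment group or any test, since the endpoint is secondary and descriptive and no inference is planned.

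The conclusion is firm for miscarriage, termination, ectopic and molar pregnancy, and open for stillbirth. It assumes that a birth with the same gaps has its birth date and gestational age recorded. The size cannot be quantified from the documents; the table above shows only how the gap behaves under assumed values of q and a borrowed outcome mix.

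**What to change.** Amend the dating paragraph of SAP 15.2 as follows.

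- **Last step.** Start of pregnancy = date of pregnancy outcome (birth, stillbirth, miscarriage, termination, ectopic or molar pregnancy) minus gestational age at that outcome, where both are recorded. Otherwise use the pregnancy-interview date minus gestational age at that interview.
- **Trigger.** Apply this step when the estimated delivery date is missing or partial, not only when it is missing.
- **Partial LMP.** If no step yields a date, assign the timing category directly when every possible LMP date lies on one side of last dose + 183 days; otherwise classify the pregnancy as undetermined.
- **Display.** Show undetermined pregnancies by outcome, so that any remaining imbalance is visible.

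The cost is one paragraph and a little programming, using items the protocol already collects. The outcome date may have to be taken from the outcome form or the adverse event record. Recovery will be partial where gestational age was derived from the missing LMP or where the outcome date is not recorded.
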